1. SYNOPSIS

Study Title	Hand-carried ultrasound for hydronephrosis	
Objective	Determine if internal medicine trainees can rapidly and accurately rule out hydronephrosis using hand-carried ultrasound	
Study Period	Planned enrollment duration: 18 months Planned study duration: 18 months	
Number of Patients	170	
Study Treatment	none	
Study Design	Prospective Observational	
Inclusion and Exclusion Criteria	
List Inclusion and Exclusion Criteria for your study:
 
Inclusion Criteria:
 
 1. Age >18 years 2. Acute kidney injury or acute kidney disease 3. Retroperitoneal ultrasound ordered or performed within the last 4 hours 
Exclusion Criteria:
 
 1. End-stage renal disease 2. History of kidney transplantation 3. Pregnant women 4. Prisoners 5. Patient unable to provide informed consent 6. Morbid obesity (BMI >40) 7. Current diagnosis of renal cell carcinoma 8. Rash overlying scanning area (left or right flank) 	
Measurements	(1) Presence or absence of hydronephrosis on hand-carried renal ultrasound (2) Severity of hydronephrosis (only when present) on HCU	
Statistical Methodology	Interobserver reliability/ kappa; Sensitivity, specificity, PPV and NPV of HCU performed by trainees compared to read by staff radiologist	

2. STUDY PROTOCOL

2.1 Background and Significance

Point-of-care ultrasound (POCUS) is an increasingly popular imaging modality that helps clinicians establish or rule out diagnoses, monitor therapy and provide real-time procedural guidance. The rapid availability, safety and low cost of POCUS have made it particularly useful in certain specialties, such as emergency medicine, critical care and trauma. The Focused Assessment with Sonography in Trauma (FAST) exam is a good example of the potential impact and wide applicability of POCUS in medical practice and is now performed worldwide and has supplemented CT as the first recommended imaging modality in the management algorithm of both stable and unstable trauma patients. POCUS is also gaining traction in medical education as an adjunct to physical examination, in the primary care setting, as well as in certain medical subspecialties.

Hand-carried ultrasound (HCU), a type of POCUS that displays images either on a smart phone or on a tablet, makes obtaining real-time imaging more portable and less cumbersome for providers who care for patients in different locations. In a study of 157 consecutive inpatients, trainee cardiologists using HCU were able to identify a normal echo in 94% and a normal EF in 100% of cases. This translated into significant reductions in cost and departmental workload.

Because renal structures are easily seen by ultrasound, enthusiasm for POCUS is increasing in the nephrology community, with terms such as “Point-of-care ultrasound in nephrology (POCUN) being recently carved out. POCUN has wide applications, including the assessment of volume status (inferior vena cava ultrasound, B-lines on lung ultrasound), hemodialysis access or obstructive kidney injury through the detection of hydronephrosis.

Renal ultrasonography is most commonly ordered for patients with acute kidney injury, with a main focus on identifying obstruction of the collecting system, a rare but potentially reversible cause of acute kidney injury. While data is lacking regarding the use of POCUS to identify hydronephrosis in an inpatient setting, data from emergency-use of POCUS demonstrates the validity of using POCUS to evaluate for hydronephrosis. In a prospective observational study of emergency department (ED) patients with suspected renal colic compared computed tomography (CT) results with POCUS and found that hydronephrosis on POCUS was predictive of a ureteral stone 88% of the time. These findings suggested that POCUS can be used to first detect hydronephrosis and aid physicians in identifying patients with renal colic¹. Another prospective observational study of emergency physicians without prior training on renal ultrasonography who underwent a short training program and then evaluated patients with presumed renal colic, acute pyelonephritis or documented renal failure with POCUS. Results of POCUS were compared with radiologist-read ultrasound and found that hydronephrosis was detected in 100% of cases and accurately ruled out in 71% of cases².

2.1.1 Preliminary Data

None available

2.2 Objective

CONFIDENTIAL: This document is the intellectual property of [name]. Acceptance of this document constitutes the agreement by the recipient that no unpublished information contained herein will be published or disclosed without prior written approval.

Evaluate the accuracy of HCU in ruling out hydronephrosis in patients with a diagnosis of acute kidney injury (AKI) or acute kidney disease (AKD) in an inpatient setting. We anticipate potential cost savings for patients and for the healthcare system.

2.3 Patient Selection

2.3.1 Inclusion Criteria

Each subject must meet all of the following criteria:

1. Age >18 years
2. Acute kidney injury or acute kidney disease
3. Retroperitoneal ultrasound ordered or performed within the last 4 hours

2.3.2 Exclusion Criteria

Subjects will not be enrolled if any of the following criteria exist:

1. End-stage renal disease
2. History of kidney transplantation
3. Pregnant women
4. Prisoners
5. Patient unable to provide informed consent
6. Morbid obesity (BMI >40)
7. Current diagnosis of renal cell carcinoma
8. Rash overlying scanning area (left or right flank)

2.4. Study Design

Observational

2.4.1 Study Procedures

CONFIDENTIAL: This document is the intellectual property of [name]. Acceptance of this document constitutes the agreement by the recipient that no unpublished information contained herein will be published or disclosed without prior written approval.

The study team will identify potential participants based on inpatient orders placed in EPIC for a radiology-performed renal ultrasound. Once an order in EPIC has been placed for a renal ultrasound to be done by radiology on a patient that is admitted to Barnes Jewish Hospital, a team member will discuss the study with participants in person.

All patients that fit inclusion/exclusion criteria will be invited to consent and take part in the study. The recruiting investigator will meet individually with each patient and describe the study to them. Patients will either be in the emergency department, on the floor (South or North campus in BJH) or in the ICU. Investigator will spend the necessary time to explain the study to each patient and answer all questions.

Patients will be told that taking part in the study is purely voluntary and that they can decline to be involved. This will not affect their medical care.

Patients will be told that they can withdraw from the study at any time after enrolling.

Team member will make sure that patients interested in study participation are in a quiet area. Team member will review the consent and answer all study related questions.

Upon consent of patient, patient's age and gender with the assigned study code number will be recorded on enrollment log. Study code number, patient name and MRN will be written on bedside data collection sheet.

One non-invasive hand-carried renal ultrasound will be performed the following way:
MD performs right and left sided renal ultrasound and notes his findings on data collection sheet and places in envelope

Each enrolled patient will have the following ultrasound images recorded within 4 hours of completion of the radiology-performed renal ultrasound:

Right kidney longitudinal view

Right kidney mid transverse view

Left kidney longitudinal view

Left kidney mid transverse view

Each clinician will record their result (presence or absence of hydronephrosis, severity of hydronephrosis if present, technical ease or difficulty in obtaining ultrasound images) on a data collection form with the study number, patient name, date and time images were acquired, clinician initials, and comment section for any other observations. The clinician will place the completed form for their measurement in an envelope with the study number on the outside.

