2.4.6 Observations and Measurements

1. Presence or absence of hydronephrosis in the right kidney
2. Presence or absence of hydronephrosis in the left kidney
3. If hydronephrosis present: severity of hydronephrosis (mild, moderate, severe)
4. Time taken to obtain ultrasound images of both kidneys
5. Technical difficulty of study as rated by operator (easy, relatively easy, challenging, very challenging)

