2.4.6.3 Primary Outcome Measures

1. Sensitivity, specificity, positive and negative predictive value of HCU compared to radiology read (blinded when obtaining data)

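### Does the plan need a stated unit of analysis, patient or kidney, before its accuracy measures can be computed?

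*Combined protocol and SAP*

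**What the plan says.** All references are to the combined protocol and SAP.

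- The Synopsis describes the main measurement without a side: "Presence or absence of hydronephrosis on hand-carried renal ultrasound". Section 2.4.1 does the same for the data form: "Each clinician will record their result (presence or absence of hydronephrosis, severity of hydronephrosis if present, technical ease or difficulty in obtaining ultrasound images".
- Section 2.4.1 also makes clear that both sides are examined: "MD performs right and left sided renal ultrasound and notes his findings on data collection sheet". It requires a longitudinal and a mid transverse view of each kidney.
- Section 2.4.6 itemises the result by side: "Presence or absence of hydronephrosis in the right kidney" and "Presence or absence of hydronephrosis in the left kidney". Severity, time taken and difficulty each appear once, with no side.
- Section 2.2 states the aim as "accuracy of HCU in ruling out hydronephrosis in patients".
- The primary outcome in section 2.4.6.3 is "Sensitivity, specificity, positive and negative predictive value of HCU compared to radiology read (blinded when obtaining data"). It names no unit.
- The heading 2.4.6.5 Statistical Methods has no text under it. Section 2.4.6.6 sets the size at 170 patients, with a specificity of 90% and a margin of 0.07. Section 2.5.2 replaces subjects who withdraw, so that enough evaluable subjects remain.

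**The concern.** Two of these descriptions read as one result per examination and one reads as two. Nothing says whether the primary measures count 170 patients or 340 kidneys, how two sides become one patient result, or whether a positive scan on the wrong side counts as a detection.

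Under an either-kidney rule, an unaffected patient is cleared only when both kidneys are read as normal. The same readings can therefore give a lower specificity by patient than by kidney. Sensitivity tends to move the other way, because a false positive on the healthy side can pass for a detection. An analyst could in principle choose the unit after seeing the data. Treating 340 kidneys as independent would also make the intervals too narrow if the two readings in a patient are correlated.

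A kidney that could not be seen has no result category of its own, because the form offers only presence or absence.

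**Working it through.** **Inputs.** From section 2.4.6.6: 170 patients, specificity 0.90, margin 0.07, alpha 0.05 and a prevalence of 90%, read here as absence of hydronephrosis. That gives 0.9 × 170 = 153 unaffected and 17 affected patients. The plan gives no within-patient correlation ρ, no share of two-sided disease and no rate of unseen kidneys. All three are assumptions below.

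**1. Does the sample size reveal the unit?** The usual precision formula is n = 1.96² × 0.90 × 0.10 / 0.07² = 70.6. Dividing by 0.9 gives 79 after rounding up, and dividing by 0.1 gives 706. Doubling the unrounded 78.4 for two kidneys gives 157. None of these is 170, so the calculation does not settle the unit. The stated count is nevertheless in patients.

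**2. How far apart can the units be?** Among unaffected patients, with an either-kidney rule and kidney specificity s, patient specificity = s² + ρ·s(1 − s).

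| Reading of the 90% | ρ = 0 | ρ = 0.5 | ρ = 1 |
|---|---|---|---|
| Kidney value 0.90: patient value | 0.81 | 0.855 | 0.90 |

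The gap is 0.09 × (1 − ρ). It exceeds the plan's 0.07 margin only when ρ < 1 − 0.07/0.09 = 0.22. If 0.90 is instead the patient value, the kidney value runs from 0.90 (ρ = 1) to √0.90 = 0.949 (ρ = 0), at most 5 points higher.

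**3. Is patient specificity always the lower one?** Only within unaffected patients. A count of all healthy kidneys also includes those opposite a diseased kidney. Suppose the 306 kidneys of unaffected patients have specificity 0.92 with both sides always read alike, and the 17 opposite kidneys have 0.70. Kidney specificity is then (281.5 + 11.9)/323 = 0.908, against 0.92 per patient.

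**4. Precision.** 95% half-width = 1.96·√(p(1 − p)/n). At 0.90 it is 0.048 for 153 patients and 0.033 for 323 kidneys treated as independent. With fully correlated kidneys it returns to 0.046. For a sensitivity of 0.90 in 17 patients it is 0.143.

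**5. Effect on ruling out.** Assume 17 patients with one-sided disease, 153 without, sensitivity and specificity 0.90 per kidney, and independent readings. By patient, any positive side counts.

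| Measure | By kidney (17 and 323) | By patient (17 and 153) |
|---|---|---|
| Sensitivity | 0.900 | 1 − 0.1 × 0.9 = 0.910 |
| Specificity | 0.900 | 0.9² = 0.810 |
| Positive predictive value | 15.3/47.6 = 0.321 | 15.47/44.54 = 0.347 |
| Negative predictive value | 290.7/292.4 = 0.994 | 123.93/125.46 = 0.988 |

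The change is mainly in specificity, and this is its largest size, at ρ = 0.

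**6. Unseen kidneys, at assumed rates u of 2%, 5% and 10% per kidney.** Coding them as absent, rather than leaving them out, changes kidney sensitivity from 0.90 to 0.90(1 − u) = 0.882, 0.855 and 0.810. Specificity rises to 0.90 + 0.10u = 0.902, 0.905 and 0.910. The largest fall in sensitivity, 0.09, is inside the half-width of 0.143.

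**The case for a change.** The strongest case for a change is that a patient count is an enrolment figure, not an analysis rule. Even if the patient is accepted as the unit, the plan does not define a positive patient or say whether sides must agree. Both units can be computed and both are defensible, which is exactly when a choice can follow the data. If the form carried only the single result without a side described in section 2.4.1, side matching might not be recoverable. For unseen kidneys the handling can also matter more than step 6 shows. If unseen counted as positive, with failures independent between sides, a patient specificity of 0.90 would become 0.90(1 − u)² = 0.86, 0.81 or 0.73 at the same three rates.

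Part of this stands: no combining rule, side-matching rule or unseen-kidney rule is written anywhere. The rest is weaker. The wording without a side never says that the result is per patient. It sits beside an instruction to scan both sides and a measurement list that names each, so it reads as shorthand for that list. Every count in the plan is in patients or subjects, and none is in kidneys. Nothing in the plan treats unseen as positive. The stored views, the difficulty rating and the comment field allow many such kidneys to be identified. Section 2.5.2 limits withdrawal to the investigator's judgement of the subject's interest or the subject's request, so a poor scan would not trigger replacement.

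**Conclusion.** No change follows. This is missing detail that an analyst can fill sensibly, not a stated rule that produces a wrong result. The plan points to the patient as the unit. The hand-carried result is to be collected for each side, and the radiology result is also collected (section 3.2.1). Calling a patient positive when either kidney is positive is an ordinary way to combine the two. Per-kidney figures can be reported alongside. No analysis that treats kidneys as independent is planned, so there is none to correct.

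On the patient reading, the 90% specificity is unaffected, and only the implied kidney value moves, by up to 5 points. The 9-point fall to 0.81 needs the less supported per-kidney reading together with zero correlation between two readings by one operator in one session. For ruling out hydronephrosis, the illustration moves sensitivity by 0.010 and negative predictive value by 0.006, both small beside a sensitivity half-width of 0.143.

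This conclusion assumes that the form follows the sided list in section 2.4.6 and that about 10% of patients have hydronephrosis. The correlation and the rates of unseen kidneys are assumed ranges, not figures from the plan.

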2.5.2 Premature Discontinuation

If a subject withdraws from the study, the subject will be replaced in order to provide the required number of evaluable subjects. Subjects will be withdrawn if the investigator decides that discontinuation is in the best interest of the subject, or the subject requests withdrawal from the study.

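### The protocol lists no HCU result for a kidney that could not be adequately seen, and no rule for counting such a scan in the accuracy measures

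*Combined protocol and SAP*

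**What the plan says.** Section 2.4.1 describes the data collection form. Each clinician records "presence or absence of hydronephrosis, severity of hydronephrosis if present", together with how easy or hard the images were to obtain, and there is also a "comment section for any other observations". The Synopsis measures the same two-way result. Section 2.4.6 lists it for each side, beginning with "Presence or absence of hydronephrosis in the right kidney", and adds "Technical difficulty of study as rated by operator (easy, relatively easy, challenging, very challenging" as a separate item. Section 2.4.1 asks for four views per patient and does not say what to do when a view cannot be obtained.

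The primary outcome (2.4.6.3) is sensitivity, specificity, PPV and NPV against the radiology read. The Statistical Methods heading (2.4.6.5) has no text under it.

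On replacement, section 2.5.2 reads: "If a subject withdraws from the study, the subject will be replaced in order to provide the required number of evaluable subjects". It gives two grounds for withdrawal: "Subjects will be withdrawn if the investigator decides that discontinuation is in the best interest of the subject, or the subject requests withdrawal". It does not define an evaluable subject.

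**The concern.** The study asks whether trainees can rule out hydronephrosis at the bedside, and it anticipates cost savings as a result. A scan that did not show the kidney has ruled nothing out. The plan foresees difficult scans: the operators are trainees, ICU patients are eligible, and only a BMI above 40 is excluded for body size. Yet the listed result has no place for a failed view.

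The difficulty rating does not fill the gap, since a very difficult scan may still be readable. A free-text comment may record the failure, but nothing carries it into the two-by-two table. The operator is left to make a call or leave the result blank, and the analyst has no rule for a blank. A call of absent made without seeing the kidney cannot reliably be told from a true negative call afterwards, so this cannot be repaired at the analysis stage.

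**Working it through.** The plan gives no failure rate and no accuracy figure that allows for failed scans, so there is no figure of its own to reproduce on this point. The planned 170 patients do not enter the calculation.

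Inputs:
- Share without hydronephrosis: 0.90 (section 2.4.6.6, reading the stated prevalence as prevalence of absence); share with hydronephrosis: 0.10.
- Specificity on seen scans: 0.90 (the target in 2.4.6.6).
- Sensitivity on seen scans: 0.90 (assumption).
- Share u of patients with an inadequate view and no positive call: not in the documents. It is assumed to be 5% to 20% and equal with and without disease. The patient is taken as the unit.

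Formulas:
- Coded absent: specificity = 0.9(1−u) + u; sensitivity = 0.9(1−u).
- Omitted: both stay at 0.90.
- Counted as not ruled out (test-positive): specificity = 0.9(1−u); sensitivity = 0.9(1−u) + u.

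| u | Specificity: absent / omitted / not ruled out | Sensitivity: absent / omitted / not ruled out |
|---|---|---|
| 5% | 90.5 / 90 / 85.5% | 85.5 / 90 / 90.5% |
| 10% | 91 / 90 / 81% | 81 / 90 / 91% |
| 15% | 91.5 / 90 / 76.5% | 76.5 / 90 / 91.5% |
| 20% | 92 / 90 / 72% | 72 / 90 / 92% |

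NPV at u = 10%:
- Coded absent: 0.9×0.91 / (0.9×0.91 + 0.1×0.19) = 0.819/0.838 = 97.7%.
- Omitted: 0.9×0.90 / (0.9×0.90 + 0.1×0.10) = 0.81/0.82 = 98.8%.
- Not ruled out: 0.9×0.81 / (0.9×0.81 + 0.1×0.09) = 0.729/0.738 = 98.8%.

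PPV at u = 10%:
- Omitted: 0.1×0.90 / (0.1×0.90 + 0.9×0.10) = 0.09/0.18 = 50%.
- Coded absent: 0.081/0.162 = 50%.
- Not ruled out: 0.1×0.91 / (0.1×0.91 + 0.9×0.19) = 0.091/0.262 = about 35%.

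Share called ruled out at u = 10% (the NPV denominators): 0.838 of attempted scans if coded absent, and 0.82 of the scans kept if omitted. With failures left in the denominator it is 0.738 of attempted scans.

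Under omission, sensitivity, specificity and NPV are the same at every u, so the reported accuracy gives no sign of how many scans failed.

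**The case against.** The strongest case against has four parts.

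First, a reader might infer that patients with unreadable scans are replaced. Section 2.5.2 does not say so: the trigger is withdrawal, and a poor image is not among the grounds. What stands is narrower. The term evaluable is undefined, and nothing says that an inadequate view is no reason for replacement.

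Second, a reader might infer that the form permits only two answers, or that the protocol prescribes a recording rule that yields a wrong result. The form is not in the documents. Section 2.4.1 describes its contents, including a comment space, and nothing tells the operator to default to absent. This is a gap in the plan, and forcing or omission is what may happen in that gap.

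Third, the size rests on an assumed failure rate, and section 2.1 says that renal structures are easily seen by ultrasound. That is fair. Moreover, at 10% the two informal routes differ by only 1 point in specificity (91% against 90%). The 10-point spread appears only against the not-ruled-out convention, so it does not measure bias in the plan. The same two routes do differ by 9 points in sensitivity (81% against 90%).

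Fourth, a forced call of absent does not flatter HCU overall. It lowers sensitivity and NPV, the measures that matter most for ruling out, and raises only specificity and the share called negative. That is correct, and the effect has to be described measure by measure.

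**Conclusion.** The point holds as a gap that should be closed. The HCU result is listed only as present or absent, no category covers a kidney that was not adequately seen, and no rule places such a scan in the primary accuracy measures. At an assumed 10% failure rate, handling alone puts specificity anywhere from 81% to 91% and sensitivity anywhere from 81% to 91%. The share ruled out is reported as 0.82 if failures are omitted, against 0.738 of all attempted scans.

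These figures assume 90% accuracy on seen scans, 10% hydronephrosis, and failures unrelated to disease. They show how far the choice can matter and do not estimate what this study will find. The gap itself does not depend on them, and it bears directly on both the rule-out question and the cost outcome.

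**What to change.** 1. In 2.4.1 and 2.4.6, add a not-adequately-visualised option for each kidney, and report the number of such scans.
2. Under 2.4.6.5, keep every attempted scan in the denominator for the share ruled out. Count a patient with an unseen kidney and no positive kidney as not ruled out.
3. Report sensitivity, specificity, PPV and NPV twice: for all attempted scans (not seen = not ruled out) and for visualised scans only.
4. In 2.5.2, define evaluable, and state that a patient whose HCU was attempted is not replaced because of an inadequate view.

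The work is one tick-box per kidney and a few sentences. The price is in the reported figures: on all attempted scans, specificity falls (81% instead of 90% at the assumed 10%) and PPV falls to about 35% from 50%. Sensitivity under this convention also credits HCU with disease it never saw (91% instead of 90%), which is why both analyses should be shown.
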